4.1.5 Blinding and procedures for unblinding

4.1.5.1 Blinding

Patients, Investigators and everyone involved in trial conduct or analysis or with any other interest in this double-blind trial will remain blinded with regard to the randomised treatment assignments until after database lock.

BI will generate and store the randomisation schedule, and prepare and code the medication in a blinded fashion. Trial supplies will be assigned to the patients via IRT.

However, due to the requirements to report suspected serious unexpected adverse reactions (SUSARs), it may be necessary for a representative from BI's drug safety group to access the randomisation code for individual patients during study conduct. In such cases, access to the code will only be permitted by authorised drug safety representatives. Access to the code will be via the IRT.

The randomisation code will be kept secret by Clinical Trial Support up to database lock. Please see Section 4.1.5.2 for the rules regarding breaking the code for an individual or for all patients in emergency situations.

4.1.5.2 Unblinding and breaking the code

In this blinded trial, an emergency code break will be available to the investigator via the IRT system. This code break may only be accessed in emergency situations when the identity of the trial drug must be known to the investigator in order to provide appropriate medical treatment or if required to assure the safety of trial participants. Each site receives a manual from the IRT provider that contains instructions on how to unblind the treatment of a patient via the IRT (via 24-hour Emergency helpline). If the code break for a patient is accessed, the Sponsor must be informed immediately. The reason for accessing the code break, together with the date, must be documented on the appropriate eCRF page. In case third party needs to break the code, however, when the investigator cannot be reached, the code can be opened by calling emergency code manager (see Emergency Code Break Manual) in the ISF.

4.1.6 Packaging, labelling, and re-supply

Boehringer Ingelheim will provide study supplies including blinded study medication and RESPIMAT inhaler training kits.

Open-label supplies= Auxiliary Medicinal Products (AMPs)

- Training RESPIMAT inhaler and placebo cartridges for training purposes are supplied. The training RESPIMAT can be used until 3 months after first insertion of the cartridge or until the device is empty. The date of the cartridge insertion should be entered on the medication label of the RESPIMAT immediately after the cartridge is inserted.

RESPIMAT inhaler for training purposes will be provided by IRT along with the initial supply order.

Blinded study medication= Investigational Medicinal Product (IMP)

- Packaging: the RESPIMAT treatment box will contain one RESPIMAT inhaler plus one drug-filled cartridge and contains sufficient medication for 30 days of treatment. The RESPIMAT inhaler will lock after 60 actuations have been administered and will no longer actuate any medication.
- Labelling: individual RESPIMAT treatment box will have a three-part tear-off label. One part of each tear-off label should be attached to the drug accountability form which will be part of the ISF, and one part will remain on the box (an extra part is available as well). The investigator or designee should fill out the following information:
 - date of cartridge insertion should be entered at time of cartridge insertion on the cover page of the cartridge booklet
 - Investigator's name should be entered at time of dispense on the cover page of the booklet on the RESPIMAT treatment box.

For details of the packaging and the description of the label, refer to the ISF.

!"#\$%&&'(

Each site will receive a first supply at or after the initiation visit and will be resupplied upon demand by IRT.

4.1.7 Storage conditions

Drug supplies will be kept in their original packaging and in a secure limited access storage area according to the recommended storage conditions on the medication label. A temperature log must be maintained for documentation.

If the storage conditions are found to be outside the specified range, CML (as provided in the list of contacts) must be contacted immediately.”

4.1.8 Drug accountability

The investigational drug storage manager will receive the investigational drugs delivered by the sponsor when the following requirements are fulfilled:

- Approval of the trial protocol by the IRB / ethics committee,
- Availability of a signed and dated clinical trial contract between the Sponsor and the head of the investigational site,
- Approval/notification of the regulatory authority, e.g. competent authority,
- Availability of the curriculum vitae of the principal Investigator,
- Availability of a signed and dated clinical trial protocol

The investigational drug storage manager must maintain records of:

- the product's delivery to the trial site,
- the inventory at the site,
- the use by each patient,
- the return to the sponsor or alternative disposition of used/unused trial medication.
- the adequate documentation that the patients were provided the doses specified by the CTP
- the reconciliation of all investigational products received from the sponsor

At the time of return to the sponsor and/or appointed CRO, the investigational drug storage manager must verify that all unused or partially used drug supplies have been returned by the clinical trial patient and that no remaining supplies are in the Investigator's possession.

The investigator/pharmacist will record on the drug accountability forms the following information.

RESPIMAT inhaler:

- dates (dispense and return),
- dispenser's initials
- batch/serial numbers,
- expiry dates,
- the unique RESPIMAT treatment box number assigned by IRT
- trial patient number assigned by the RDC system.

See [Section 4.1.2](#) for the randomisation. It is important to enter the date of priming on the medication label of the RESPIMAT.

Rescue medication (salbutamol MDI prescribed at sites) and training RESPIMAT:

AMP accountability form for each will be provided to the trial site. This record will include:

- dates (dispense and return)
- dispenser's initials
- quantities,
- batch/serial numbers,

- expiry date,
- the trial patient number assigned by the RDC system.

The patient will be asked to return all used/unused rescue medication inhalers at each clinic visit. Source data documentation and full drug accountability in regard to dispensed and returned medication to investigational site and to patients are required. Only used inhalers will be replaced at each clinic visit. For further details, please refer to Section 4.2.1 (Rescue medication).

4.2 CONCOMITANT THERAPY, RESTRICTIONS, AND RESCUE TREATMENT

4.2.1 Rescue medication, emergency procedures, and additional treatment(s)

4.2.1.1 Rescue Medication

Administration of rescue medication can occur at any point during the trial as deemed necessary by the patient or the investigator. Salbutamol will be prescribed as rescue medication in the trial site; only the salbutamol prescribed in the trial site is allowed for rescue medication use. If the patient requires rescue medication during the pulmonary function test (PFT) days (Visits 1, 2, 3, and 4), the PFTs will be discontinued. The visit should be rescheduled if possible. The medication used, route and 24-hour clock time of administration will be recorded on the Rescue Medication eCRF page.

4.2.1.2 Emergency procedures

There are no special emergency procedures to be followed.

4.2.1.3 Additional treatments

Medications allowed to controlling acute exacerbations as medically necessary during the treatment period:

- Salbutamol inhalation aerosol from MDI for p.r.n. use
- Temporary increases in the dose or addition of oral steroids are allowed during the treatment portion of the study. PFT should not occur within 7 days of the last administered dose of an increase or addition of oral steroids. These tests may be postponed up to 14 days to meet this restriction. Subsequent visits will be scheduled according to the patient's regular schedule.
- Temporary additions of theophylline preparations are allowed during the treatment portion of the study. PFT should not occur within seven days of the last dose. These tests may be postponed up to 14 days to accommodate this restriction. Subsequent visits will be scheduled according to the patient's regular schedule.

- The use of antibiotics is not restricted and may be prescribed as medically necessary for exacerbations and / or infections. If antibiotics are prescribed for a respiratory infection prior to PFT, these tests will be postponed for at least 2 days but not more than 7 days after the last dose is given. Subsequent visits will be scheduled according to the patient's regular schedule.

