- ⁴ A preliminary check of in-/exclusion criteria is recommended at Visit 0 to avoid unnecessary washout procedures in non-eligible patients.
- ⁵ To be performed only if relevant findings at Visit 4/EOT.
- ⁶ Women of child-bearing potential: pregnancy test at Visit 1 and Visit 4/EOT
- ⁷ The patient will be instructed in the use of the RESPIMAT, but patient **should not** inhale from the training inhaler at Visit 2.
- ⁸ Rescue medication as salbutamol is prescribed at visit 0. Rescue medication will be collected and prescribed on subsequent visits by investigators as needed. All rescue medication for the trial to be confirmed to be collected at Visit 4/EOT.
- ⁹ Pre- and post-bronchodilator (400 µg salbutamol) [note: reversibility is not an inclusion criterion], Spirometry measurement; FVC and FEV₁ only.
- ¹⁰ Baseline spirometry measurement FEV₁, FVC, SVC, and IC.
- ¹¹ Morning post-dose spirometry

Proprietary confidential information © 2015 Boehringer Ingelheim International GmbH or one or more of its affiliated companies

- FEV₁ and FVC: 30 min post-morning dose as starting time
- IC and SVC measurement: 60 min post-morning dose as starting time

12
13

Prior to the start of PFTs are performed.

[REDACTED]

14

Patients should wear and measure activity monitor (3-axis accelerator) every day for 2 weeks prior to Visit 2, Visit 3 and Visit 4/EOT.

15

[REDACTED]

16

17

Site staff will telephone the patients 15 days and 8 days prior to the next planned Visit and remind them to wear physical activity monitor every day. An assessment of adverse events and of concomitant therapy should be performed from the last assessment.

18

Trial medication dispensed at Visit 2 should be administrated at clinic at Visit 3 and trial medication dispensed at Visit 3 should be administrated at clinic at Visit 4/EOT. Newly assigned trial medication at Visit 3 should be administered next day of Visit 3.

19

[REDACTED]

20

Refer to [Appendix 10.8. mMRC](#)

21

Training of 6MWT

22

Refer to [Appendix 10.11](#)

23

Training of patient diary at Visit 1. Dispense of the diary at Visit 1, Visit 2 and Visit 3. Reviewing and collection of the diary at Visit 2, Visit 3 and Visit 4/EOT.

TIMING OF PROCEDURES: VISIT1_SCREENING

	Start time					
	-	More than 30 min prior to Pre-dosing PFT	-10 to 0 min prior to administration salbutamol	administration salbutamol (0 min)	10 to 15 min after administration salbutamol	-
Medication washout compliance	X					
mMRC ¹	X					

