3.2 DISCUSSION OF TRIAL DESIGN, INCLUDING THE CHOICE OF CONTROL GROUP(S)

Since patients may be randomised to a treatment arm that includes both a LABA (olodaterol) and a LAMA (tiotropium), it is necessary to restrict the use of LABA (e.g. salmeterol, formoterol, indacaterol) and LAMA or SAMA (e.g. tiotropium, ipratropium) during the treatment period. Patients will continue to receive treatment with inhaled corticosteroids as required. SABA medication (salbutamol MDI) will be prescribed at the trial site to all patients for rescue use, and appropriate medications will be allowed to control acute exacerbations as medically necessary.

A 6-week treatment period is considered sufficient to evaluate the effects of tiotropium + olodaterol FDC at pharmacodynamic steady state (based on results from previous studies evaluating the effects of tiotropium + olodaterol FDC on spirometric parameters).

The cross-over design allows for each patient to serve as his/her own control. As such, treatment comparisons are within patient rather than between patients, which removes the inter-patient variability from the comparison between treatment regimens [[R94-1529](#)].

Patients participating in this trial should perform exercise tolerance test for every visit. In order to decrease the burden on patients, medication restrictions such as a longer washout period have not been included in this trial. All participants are treated with tiotropium in both treatment periods, so a washout period for tiotropium before treatment 2 has not been included in this trial. In terms of olodaterol, we set the efficacy endpoints in the 2 weeks prior to Week 6 in order to avoid a carryover effect of olodaterol in the previous period. It is also considered sufficient to evaluate the effects of tiotropium + olodaterol FDC at the efficacy endpoints in the 2 weeks prior to Week 6 because a pharmacodynamic steady state of olodaterol has been reached.

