6. INVESTIGATIONAL PLAN

6.1 VISIT SCHEDULE

This trial consists of a screening period, two period 6-week treatment periods, and a 3-week follow-up period. Following the screening visit (Visit 1) and 2-week screening period, patients will be randomised into the first of double-blind treatment period (Visit 2).

Additional clinic visits will be scheduled after 6 weeks of treatment (Visits 3 and Visit 4/EOT) and once 3 weeks post-treatment (Visit 5).

Patients should make every attempt to complete the protocol as specified. Investigators should encourage patient treatment compliance and adherence to other protocol specific activities. All deviations from the planned visit schedule will be documented. Refer to the [Flow chart](#) for time windows for the visits.

Rescheduling in general

A patient may be rescheduled twice (within one week of the scheduled visit date) due to lack of medication washout compliance or no intake of study medication on the day preceding the clinic visit.

Rescheduling after randomisation

Subsequent visits should always be planned to take place to assure a minimum 6 week treatment period.

If rescheduling of visits after randomisation is necessary, the total daily doses of the RESPIMAT inhaler need to be obeyed. Reserve medication is dispensed at each treatment period to avoid intermediate visits.

If rescue medication is administered during a visit day within 8 hours prior to administration of trial medication, the visit will be rescheduled once. Further rescheduling should be discussed with the local clinical monitor.

Refer to [Section 4.2.1](#) for details on medications allowed to control acute COPD exacerbations and restrictions for these medications prior to PFTs.

In case a visit needs to be rescheduled outside the allowed time window (e.g. in order to meet PFT washout requirements following treatment of an acute exacerbation), the CML should be contacted.

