6.2 IMPORTANT PROTOCOL VIOLATIONS

A patient's deviation from the trial protocol is considered "important" if it can be expected that the deviation had a distorting influence on the assessment of the treatment effect on the primary endpoint of the trial or could affect the patient's safety/rights.

[Table 6.2: 1](#) lists the important PVs for this trial. Some of the important PVs can be checked automatically through the electronic case report form or through programming of relevant data in the database; others will need information gained from investigator comments or site monitoring reports and will need a decision at a Medical Quality Review Meeting (MQRM) or BRPM or through team review of the manual PV log.

In the case that a patient was randomised in both this trial and another trial or was randomised at two different sites in this trial, the patient will be indicated as having an important PV (IPV, see [Table 6.2: 1-Exclusion Criterion 27](#)). The following process will be followed with regards to the patient's data.

- All efficacy data will be excluded from the analysis and the patient will be excluded from the Full Analysis Set (FAS) (for this trial or both trials as appropriate).
- The only safety data which will be reported is exposure and serious adverse events (SAEs). These will be analysed according to the treatment which the patient actually received. If the patient was randomised twice in this study and both treatments are the same, the patient's data will be combined (i.e. the patient is only counted once). If the patient participated in two different trials in the same project, he/she will be reported separately for each trial. As well, care will be taken with regard to the SAE narratives as to whether data for one patient number is relevant for an SAE under the other patient number.
- For disposition, demographics, baseline characteristics and important PVs, the patient will be analysed as treated. If the patient was randomised twice in this study and the treatments are different, the patient will be counted under each treatment. A footnote will be included in the disposition table identifying the situation and noting that the patient is counted twice for disposition as well as demographics, baseline data and important PVs.

The final decision with regards to important PVs and exclusion from the PPS will be made at the final BRPM or database lock meeting before unblinding.

Table 6.2: 1 Important protocol violations

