Category/ Code	Description	Example/Comment	Excluded from	Automatic/ Manual
A	Entrance criteria not met			
A1	Inclusion criteria violated	Inclusion Criteria 2,3,4,5,6,7,8 not met	Exclude from PPS: 2,3,4,5,6,7,8	Criteria 3 ,5 and 6 are Automatic. Otherwise Manual.
A2	Exclusion criteria violated	Exclusion Criteria 2-14,16-29 not met	Exclude from PPS: 3,9-14,17-20,23,27,28 Keep in PPS: 2,4-8,15, 16, 21, 22, 24-26,29	Manual
B	Informed consent			
B1	Informed consent not available/not done			
B1.1	Informed consent to study not available/not done	Informed consent date missing; no signature on ICF.	All	Manual
B2	Informed consent too late	Date of informed consent was after a patient signed the correct version of the ICF after Visit 0, such cases will be discussed at MQRM/BRPM/DBL meetings.	None	Automatic

ICF = Informed Consent Form

DBL = Database Lock

BRPM = Blinded report planning meeting

MQRM = Medical Quality Review Meeting

PPS = Per protocol set

Table 6.2: 1 (cont'd) Important protocol violations

Category/ Code	Description	Example/Comment	Excluded from	Automatic/ Manual
C	Trial medication and randomisation			
C1	Incorrect trial medication taken	Not throughout study; could be at a clinic visit or between clinic visits. External vendor will check before unblinding.	PPS (decision at BRPM)	Automatic and Manual
C2	Randomisation order not followed and incorrect trial medication taken	Throughout the study	PPS	Automatic and Manual
C3	Non-compliance with study medication			
C3.2	Serious non-compliance with study medication as reported in monitoring report or manual PV spreadsheet	Decision at BRPM/MQRM.	PPS if at Visit 3 or 4	Manual
C4	Medication code broken inappropriately	To be discussed and decided during MQRM/BRPM. Only inappropriate code breaks are IPVs (e.g. unblinding by Global Pharmacovigilance is not).	PPS	Manual
D	Concomitant medication			
D1	Improper medication washout at baseline visit or primary endpoint visit(s)	Visit 2, 3 or 4. Refer to Table 4.2.2.1: 1 in CTP. Decision at BRPM	PPS	Manual
D2	Prohibited medication use during study	Check CT. Decision at BRPM.	PPS if in the week prior to Visit 3 or Visit 4	Manual
F	Incorrect timing			
F3	Primary endpoint recorded outside time window			
F3.6	PFT measurement at 60 minutes planned time taken <30 minutes or > 3 hours after dosing	Visit 3 or 4	PPS	Automatic

CT = Concomitant Therapy

BRPM = Blinded report planning meeting

MQRM = Medical Quality Review Meeting

PPS = Per protocol set

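### Can a postponed Visit 3 leave period 2 shorter than six weeks, with nothing in the SAP to catch it?

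*Protocol*

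**What the plan says.** Protocol Section 4.2.1.3 allows temporary oral steroids or theophylline for an acute exacerbation and keeps lung function tests at least 7 days clear of the last dose. For oral steroids it then says: "These tests may be postponed up to 14 days to meet this restriction. Subsequent visits will be scheduled according to the patient's regular schedule". Theophylline has the same 14-day limit. Antibiotics have their own limit of 2 to 7 days after the last dose. All three rules return later visits to the patient's regular schedule, a term the protocol does not define.

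The flow chart puts Visit 3 on Day 43 and Visit 4 on Day 85, each with a window of +3 days. Its footnote 18 adds: "Newly assigned trial medication at Visit 3 should be administered next day of Visit 3".

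Protocol Section 6.1, on rescheduling after randomisation, says: "Subsequent visits should always be planned to take place to assure a minimum 6 week treatment period". On visits that must leave their window, it gives as its example a move "in order to meet PFT washout requirements following treatment of an acute exacerbation), the CML should be contacted".

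There is no washout between periods. Section 3.2 defends this by timing: "we set the efficacy endpoints in the 2 weeks prior to Week 6 in order to avoid a carryover effect of olodaterol". It considers that interval long enough for the combination "because a pharmacodynamic steady state of olodaterol has been reached".

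In the SAP, Section 6.2 treats a deviation as important if it can be expected that "the deviation had a distorting influence on the assessment of the treatment effect on the primary endpoint", or if it could affect the patient's safety or rights. The one visible timing code in Table 6.2: 1 is F3.6: "PFT measurement at 60 minutes planned time taken <30 minutes or > 3 hours after dosing". Table 6.7: 1 derives the actual day of Visit 4 from the Visit 3 date (planned day 43) and also from the Visit 2 date (planned day 85).

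**The concern.** Read alone, the postponement rule seems to let a site delay Visit 3 by two weeks and still hold Visit 4 on its original date. Period 2 would then absorb the whole delay, and a value taken after about four weeks would enter the primary analysis as a value after six weeks. With no washout, the defence against olodaterol carryover rests on measuring late in each period, so a shortened period 2 touches the design's main safeguard. The affected patients would be those treated for an exacerbation near the end of period 1, so they would not be a random subset.

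The SAP appears to offer no dedicated protection. F3.6 concerns time since dosing on the test day, not days on treatment. The per-protocol analysis might not help either, because it is run only when that set falls below 90% of the full analysis set, and Table 6.3: 1 plans it for the primary endpoint alone.

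**Working it through.** **Inputs.** Visit 3 on Day 43, Visit 4 on Day 85, window +3 for each (flow chart). Period-2 dosing starts the day after Visit 3 (footnote 18). Six weeks is taken as 42 daily doses. Maximum postponement is 14 days (Section 4.2.1.3). I assume that Visit 3 moves as a whole, since its tests are done on period-1 drug.

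**Plan's own figure.** 85 − 43 = 42 days between visits, and 85 − 43 + 1 = 43, which matches the planned period day in SAP Table 6.7: 1.

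**Calendar reading.** Let Visit 3 slip by s days, to Day 43 + s.

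- First period-2 dose: Day 44 + s.
- Doses up to and including Visit 4 on Day D: D − 43 − s, which is 42 − s on Day 85 and 45 − s on Day 88.
- SAP actual day of Visit 4: 43 − s or 46 − s.
- Keeping 42 doses needs Visit 4 on Day 85 + s or later.

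| Slip s | Doses by Day 85 / Day 88 | SAP actual day | Visit 4 for 42 doses |
|---|---|---|---|
| 3 | 39 / 42 | 40 / 43 | Day 88 (in window) |
| 4 | 38 / 41 | 39 / 42 | Day 89 (1 day late) |
| 7 | 35 / 38 | 36 / 39 | Day 92 (4 days late) |
| 14 | 28 / 31 | 29 / 32 | Day 99 (11 days late) |

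From 45 − s ≥ 42, the window and the six-week minimum are compatible up to s = 3 and incompatible from s = 4, provided the window stays fixed to study Day 85.

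**Section 3.2's interval.** On schedule, Visit 4 is period-2 day 42, so the two weeks before it are period-2 days 28 to 41. After a 14-day slip on the calendar reading:

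- Inspiratory capacity is measured on period-2 day 28 (Day 85) or 31 (Day 88). Both lie inside days 28 to 41.
- Activity is averaged over days 14 to 27, or 17 to 30. That leaves 0 or 3 of the 14 days inside the interval.

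**Interval reading.** If Visit 4 is counted from the actual Visit 3 date, period 2 keeps its 42 doses for any s and the conflict disappears. Several provisions work with this reading:

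- Section 6.1 attaches the word always to the six-week minimum and names washout after exacerbation treatment as a reason to leave the window.
- SAP Table 6.7: 1 counts Visit 4 from the actual Visit 3 date.
- Activity monitoring is tied to the two weeks before the visit, and the telephone reminders to 15 and 8 days before the next planned visit, so both move with it.
- Supply is no obstacle. Section 4.1.4 assigns three boxes per period, one of them a reserve, and each holds 30 days of treatment. A period 1 lengthened by 14 days needs 57 doses (Day 1 to Day 57), and two boxes hold 2 × 30 = 60. Extra inhalers can be requested for rescheduled visits.

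**Detection.** A short period 2 appears directly in the actual-day variable, for example 29 or 32 against 43. Section 6.1 requires all deviations from the visit schedule to be documented. SAP Section 6.2 defines importance by distortion of the primary comparison, and code Z2 removes such a patient from the per-protocol set after blinded review.

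**The case for a change.** The best argument for a change is that neither section overrides the other. Section 6.1 sends the reader back to Section 4.2.1, where the regular-schedule sentence stands. For out-of-window visits it says only to contact the monitor, with no limit and no statement of which date anchors Visit 4. The SAP counts Visit 4 from both Visit 3 and Visit 2, so it does not choose either. A site could follow Section 4.2.1.3 to the letter and produce a 28-dose period 2. The full analysis set would keep that value, and Z2 depends on someone noticing. The per-protocol run is not assured: with 180 patients in the full analysis set, the trigger is fewer than 0.9 × 180 = 162, which takes at least 19 exclusions.

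Much of this stands. The term is undefined, the two sections are not cross-referenced on this point, and no visible code covers days on treatment. What does not stand is the claim that a site cannot comply, because Section 6.1 itself provides the way out of the window. Nor is there documented harm. The number of patients and any dilution of the effect are not given, so a power figure would rest on invented inputs. Section 3.2 says steady state holds in the last two weeks; it does not say that carryover persists before then, so distortion of the activity averages is an inference. SAP Section 4 and the activity analysis subsections are redacted, so nothing can be said about what further checks they hold. The 90% trigger is a general feature of the plan, and exclusions under the other codes count towards it as well.

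**Conclusion.** No change to the plan follows. The arithmetic is right as far as it goes: on a fixed calendar, a Visit 3 slip of 4 days or more costs period-2 treatment, down to 28 to 31 doses at the 14-day limit. That outcome requires a site to apply Section 4.2.1.3 while passing over Section 6.1, which states the six-week minimum and names this situation. Taken as a whole, the protocol lets a site and its monitor handle the case sensibly, and the SAP gives the blinded review a variable that shows any exception.

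The likely effect on the primary endpoint is small, because even the extreme case has inspiratory capacity measured within the interval that Section 3.2 regards as steady state. This rests on that premise, on sites contacting the monitor as Section 6.1 asks, and on Visit 3 moving as a whole. For the activity endpoints the shift could be larger in an affected patient, but its frequency and size cannot be derived from the documents.

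The wording of the two sections and the flow-chart window should be reconciled. Which date anchors Visit 4 is for the sponsor and is not decided here. That is editorial: the endpoint, the analysis sets, the model and the primary conclusion stay as planned. A dedicated violation code would affect only a supportive analysis, for cases that Z2 already allows the blinded review to take up.
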